3.3 Study population

The study population will comprise of YLWH aged 15 -24 years who are ART naïve or on ART since Jun 2019.

Target population:

Youth living with HIV registered to receive ART at any of the 3 ART clinic in Kiryandongo district :Kiryandongo Hospital, Panyandoli HCIII and Nyakadoti HCII

Accessible population:

[figure not shown]
Youths consented/assented for CFLU, registered for care at Kiryandongo hospital, Panyadoli HCIII or Nyakadoti CII.

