$Z_{\alpha/2}$ = standard normal deviate for two-tailed test based on alpha level (relates to the confidence interval level)

Z_{β} = standard normal deviate for one-tailed test based on beta level (relates to the power level)

r = ratio of controls to cases

p_1 = proportion of cases with exposure and $q_1 = 1-p_1$

p_2 = proportion of controls with exposure and $q_2 = 1-p_2$

$$\bar{p} = \frac{p_1 + rp_2}{r+1} \quad \text{and} \quad \bar{q} = 1 - \bar{p}$$

The sample size formula *without* the correction factor by Fleiss is:

$$n_{\text{UC}} = \frac{n_1}{4} \left[1 + \sqrt{1 + \frac{2(r+1)}{n_1 \tau |p_2 - p_1|}} \right]$$

[figure not shown]
$$n_{\text{2x}} = r n_{\text{UC}}$$

When the input is provided as an odds ratio (OR) rather than the proportion of cases exposed, the proportion of cases exposed is calculated as:

$$p_1 = \frac{p_2 \text{OR}}{1 + p_2(\text{OR} - 1)}$$

Sample Size: X-Sectional, Cohort, & Randomized Clinical Trials (OpenEpi, 2019) (<https://www.openepi.com/SampleSize/SSCohort.htm>)

Two-sided significance level (1- α):	95
Power (1- β , % chance of detecting):	80
Ratio of sample size, Unexposed/Exposed:	1
Percent of Unexposed with Outcome:	79
Percent of Exposed with Outcome:	94 (Jessica E. Haberer et al., 2013)
Odds Ratio:	4.2
Prevalence Ratio:	1.2
Prevalence difference:	15

	Kelsey	Fleiss	Fleiss with CC
Sample size- Exposed(intervention):	81	80	93
Sample Size-Nonexposed (Control):	81	80	93
Total Sample Size:	162	160	186

CC= continuity correction. Results are rounded up to the nearest integer.

Calculation output:

[Expand All](#) | [Collapse](#)

- [Home](#)
- [Info and Help](#)
- [Language/Options/Settings](#)
- [Calculator](#)
- [Counts](#)
 - [Std.Mort.Ratio](#)
 - [Proportion](#)
 - [Two by Two Table](#)
 - [Dose-Response](#)
 - [R by C Table](#)
 - [Matched Case Control](#)
 - [Screening](#)
- [Person Time](#)
 - [1 Rate](#)
 - [Compare 2 Rates](#)
- [Continuous Variables](#)
 - [Mean CI](#)
 - [Median/Percentile CI](#)
 - [t test](#)
 - [ANOVA](#)
- [Sample Size](#)
 - [Proportion](#)
 - [Unmatched CC](#)
 - [Cohort/RCT](#)
 - [Mean Difference](#)
- [Power](#)
 - [Random numbers](#)
- [Searches](#)
 - [Google--Internet](#)
 - [PubMed--MEDLARS](#)
 - [Internet Links](#)
 - [Download OpenEpi](#)
- [Development](#)

[Start](#) | [Enter](#) | [Help](#) | [Examples](#)

Sample Size:X-Sectional, Cohort, & Randomized Clinical Trials

Two-sided significance level(1-alpha):	95
Power(1-beta, % chance of detecting):	80

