Ratio of sample size. Unexposed/Exposed:	1
Percent of Unexposed with Outcome:	79
Percent of Exposed with Outcome:	94
Odds Ratio:	4.2
Risk/Prevalence Ratio:	1.2
Risk/Prevalence difference:	15

	Kelsey	Fleiss	Fleiss with CC
Sample Size - Exposed	81	80	93
Sample Size-Noneexposed	81	80	93
Total sample size:	162	160	186

References

Kelsey et al., Methods in Observational Epidemiology 2nd Edition, Table 12-15
 Fleiss, Statistical Methods for Rates and Proportions, formulas 3.18 & 3.19
 CC = continuity correction
 Results are rounded up to the nearest integer.
 Print from the browser menu or select, copy, and paste to other programs.

Results from OpenEpi, Version 3, open source calculator--SSCohort
 Print from the browser with ctrl-P
 or select text to copy and paste to other programs.

MAKERERE UNIVERSITY
 SCHOOL OF MEDICINE
 RENEWAL
 VALID UNTIL

★ 10 FEB 2023 ★

RESEARCH & ETHICS COMMITTEE
 103 FOR EACH ARM, KAMPALA

Factoring 10% loss to follow-up, the total sample size will be 206(103 for each arm, KAMPALA)

[figure not shown]
Data collection procedures:

The intervention is mobile phone based IVR. However, the CLFU trial found that, it was observed that a good number of participants (50 of 256) at the urban site were not enrolled due to absence of a basic mobile phone, or had malfunctioning phone keyboards (for Poster Exhibition at the 20th International Conference on AIDS and STIs in Africa (ICASA 2019). Therefore, we shall provide a basic mobile phone to everyone in the study (SoC and intervention arm). To avoid stigma associated with a particular phone, we shall get 4 or more types of basic phones. Issues regarding simcard registration will be dealt with by the individuals.

Four study questionnaires will be administered at baseline and 6-monthly until the 12-month exit visit.

The questionnaires will capture:

- Sociodemographic and medical history
- Stigma scores
- Knowledge assessment
- Sexual behavior assessment
- Knowledge of COVID-19 (only at baseline)

The data will be entered using REDCap. Blood for viral load will be collected at baseline and at the 6 and 12-month visit.

Intervention: mHealth CFLU tool

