Descriptive analysis will be done for the factors that influence adherence, virological suppression, stigma and retention in care. In addition, the distribution of the independent variables will be done with categorical data summarized using frequencies and percentages. Numerical data will be summarized using means and standard deviations for normally distributed data, and median and inter-quartile range for data that is not normally distributed.

Bivariate Analysis

The relationship between independent variables (age, gender, ART duration, marital status, education status, occupation and religion) and adherence and virological suppression will be analyzed using bivariate analysis made using cross tabular analysis and associations investigated using the Pearson Chi-square test.

The Chi-square test is based on the computational formulae below:

$$\chi^2 = \sum_{i=1}^r \sum_{j=1}^c \frac{(O_{ij} - E_{ij})^2}{E_{ij}}$$

Where

r is the number of categories of the ith explanatory variable

c is the number of categories of the dependent variable

[figure not shown]
O_{ij} is the observed number of observations in the ith explanatory

and jth dependent variable

E_{ij} is the expected number of observations in the ith explanatory?

and jth dependent variable

Further, odds ratios shall be used to analyze the relationship between the dependent variable and the independent variables. Variables found to be significant at p value of p ≤ 0.05 will be considered for the multivariable analysis.

Multivariate Analysis

Multivariable logistic regression will be used to determine the factors that influence adherence or virological suppression and retention in care. Variables found to be statistically significant at $p \leq 0.05$ in bivariate analysis and those considered to have a scientific explanation will be entered into the multivariable model.

The multivariate logistic regression adopted is based on the formulae below:

$$\ln \left[\frac{p_i}{1 - p_i} \right] = \beta_0 + \beta_1 X_1 + \dots + \beta_n X_n$$

[figure not shown]
Where;

X = independent variables

p_i = Probability of being adherent and virally suppressed

$1 - p_i$ = Probability of non-adherence or not suppressed virologically

β_0 = constant ; β_i = coefficient of the determinant

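### Viral load is measured at baseline in both arms, but adjusting the month 6 and month 12 suppression comparison for it is left to a p-value screen or judgement, not pre-specified

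*Combined protocol and SAP*

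**What the plan says.** All places are in the combined protocol and SAP.

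- **Measurement.** Section 3.4, Data collection procedures: "Blood for viral load will be collected at baseline and at the 6 and 12-month visit". The enrolment and registration steps send participants of both arms for the blood draw, at the same visit but after the allocation envelope is opened.
- **Sizing.** The sample size table in 3.4 uses suppression as the outcome: "Percent of Unexposed with Outcome: 79" and "Percent of Exposed with Outcome: 94". Section 2.6 confirms that suppression is the proxy for adherence.
- **Population.** Section 3.3: "YLWH aged 15 -24 years who are ART naïve or on ART since Jun 2019". Participants already on treatment and participants starting it enter together, and the proportions are not given.
- **Analysis.** The Bivariate Analysis paragraph lists "independent variables (age, gender, ART duration, marital status, education status, occupation and religion) and adherence and virological suppression". The Multivariate Analysis paragraph adds: "Variables found to be statistically significant at $p \leq 0.05$ in bivariate analysis and those considered to have a scientific explanation will be entered". Its stated purpose is to find factors that influence adherence, suppression and retention. Study arm is not on the list, and neither is baseline viral load.
- **Arm comparison.** Study Objective 3, Health outcomes, says that the numbers suppressed in each arm at months 6 and 12 will be compared. It gives no test, model or effect measure. Survival curves of time to suppression are also planned for each arm. The present point concerns the comparison at fixed visits, not those curves.

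**The concern.** The outcome's own baseline value is usually one of its best predictors. The documents suggest that this holds here. Section 1.2 cites low suppression among ART-treated children with virological failure even after the recommended counselling. Table 1 shows that both kinds of youth exist at the main site, with 208 suppressed and 52 unsuppressed results in June 2019.

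The entry rule mixes three groups with different prospects: on ART and suppressed, on ART and unsuppressed, and ART naive or just starting. ART duration is on the list, but it does not separate the first two. Because the baseline sample is drawn after allocation, randomisation cannot have been stratified on its result. Analysis is therefore the only place where that result can be used.

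Two things are at stake: some precision in the CFLU v SoC estimate, and protection if the arms differ by chance in the share already suppressed.

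**Working it through.** **Inputs from the plan.** "Two-sided significance level (1- α): 95"; "Power (1- β , % chance of detecting): 80"; 79% v 94%; 1:1 allocation; 93 evaluable per arm, raised to 103 for 10% loss to follow-up.

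**Inputs not in the plan (assumed).** The case mix at entry, and the link between baseline and later suppression.

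**1. The plan's own figure.** Mean proportion = (0.94 + 0.79)/2 = 0.865.
- Kelsey: (1.96 + 0.8416)² × 0.865 × 0.135 × 2 / 0.15² = 81.5 per arm (plan: 81).
- Fleiss: 80.3 (plan: 80). With continuity correction: 93.1 (plan: 93).
- 93 × 1.10 = 102.3, rounded up to 103 per arm, 206 in total.

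The stated sample size reproduces, and it does not rely on covariate adjustment.

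**2. Unadjusted power at 93 per arm.** z = 0.15/√(0.79 × 0.21/93 + 0.94 × 0.06/93) = 3.068, so power = Φ(3.068 − 1.96) = 86.6%. The pooled-variance form gives 85.5%. Simulated tests give about 87% to 88%.

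**3. Power with a three-level baseline factor (simulation, 93 per arm).** The arm effect was set to give 94% overall in CFLU. The model was a linear risk-difference model with robust standard errors.

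| Assumed mix and control suppression | Power without | Power with |
|---|---|---|
| Strong separation: 60% on ART suppressed (92%), 20% on ART unsuppressed (40%), 20% naive (79%) | 87.7% | 92.2% |
| Half the sample naive | – | gain about 2 to 3 points |
| Mild separation: same mix, 85%, 60%, 80% | 88.4% | 89.5% |

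Both fully specified mixes average 79% in control: 0.6 × 0.92 + 0.2 × 0.40 + 0.2 × 0.79 = 0.79, and 0.6 × 0.85 + 0.2 × 0.60 + 0.2 × 0.80 = 0.79. A separate run with milder separation gave about 0 points. With small-sample (HC3) standard errors, type I error was 5.0% with and without the factor. A simulation whose robust errors were not described as HC3 gave 5.9% with the factor and 5.2% without.

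**4. Cross-check with a two-level factor.** Likelihood-ratio test for arm in logistic regression, 3,000 trials per row, marginal rates held at 79% and 94%. The odds ratio (OR) is for later suppression, baseline suppressed v unsuppressed.

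| Suppressed at baseline | OR | Power without | Power with |
|---|---|---|---|
| 50% | 1 | 87.8% | 88.1% |
| 50% | 3 | 87.9% | 89.4% |
| 50% | 6 | 87.9% | 90.6% |
| 50% | 10 | 88.0% | 90.7% |
| 79% | 1 | 88.3% | 88.5% |
| 79% | 3 | 88.0% | 88.7% |
| 79% | 6 | 88.2% | 91.8% |
| 79% | 10 | 86.8% | 92.0% |

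Steps 3 and 4 agree on a gain of about 0 to 5 points. In step 4 the conditional odds ratio for arm runs from 4.16 (no association) to 5.35 (last row) with the marginal rates unchanged. The effect measure therefore has to be stated.

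**5. Chance imbalance.** The SD of the between-arm difference in baseline suppression is √(2p(1 − p)/93).
- p = 0.50: SD 0.073; 0.10/0.073 = 1.36 SD; two-sided probability about 17%.
- p = 0.79: SD 0.060; 0.10/0.060 = 1.67 SD; about 9%.

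Simulation gives about 16% and 8% to 9%.

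**6. Effect of an imbalance.** If later suppression differs by 20 to 40 points between participants suppressed and unsuppressed at baseline, a 10-point imbalance moves the unadjusted difference by 0.10 × 0.20 = 2 points to 0.10 × 0.40 = 4 points. The target is 15.

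**The case against.** **The list is not the covariate set of an arm model.** This stands. The section describes a search for associated factors and names no arm effect. A reader might infer that the plan has an arm model that wrongly leaves out baseline viral load. In fact no such model is written, which is the larger gap, and the fix has to supply one.

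**The benefit is not lost.** This also stands. The clause on scientific grounds would let an analyst enter baseline viral load. A reader might infer that adjustment is ruled out, but the text only leaves it to discretion.

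**The gain is assumption-driven.** This stands, and it is why only a range is given. In the strong scenario the naive rate equals the on-ART average, (0.6 × 0.92 + 0.2 × 0.40)/0.8 = 79%. Naive v on-ART status is then uninformative by construction, and adjusting for it alone gave 87.5%, which is no gain. Where ART duration does predict suppression, the extra gain from baseline viral load would be smaller. A single-correlation variance formula would suggest more, but the implied correlation in that scenario is 0.49 in SoC and only 0.32 in CFLU, where suppression is near its ceiling.

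**Stratification might already help.** This stands in part. The enrolment text points to randomisation details that do not appear in the text available, so stratification by ART status cannot be excluded. Stratification on the baseline sample's result can be, from the order of procedures.

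**Randomisation makes the unadjusted comparison valid.** Correct. Nothing here shows bias in the design or a shortfall against the stated 80% power.

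**Conclusion.** The point holds as a modest, nearly free improvement. A prognostic measurement is collected from everyone, and the plan does not commit to using it in the comparison that matters most. The low end of the power range applies if baseline groups differ mildly in outcome, and the high end if on-ART unsuppressed youth do much worse than suppressed ones. The imbalance frequencies assume that 50% to 79% are suppressed at entry. The documents give neither that share nor the strength of the association, so no single figure for the gain can be claimed.

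**What to change.** In the Multivariate Analysis paragraph of 3.4, cross-referenced from Health outcomes under Study Objective 3, state that:

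- suppression at month 6 and at month 12 is compared between CFLU and SoC in a model containing study arm and a three-level baseline factor: on ART with viral load below 1000 copies/mL; on ART with 1000 or above; ART naive or just initiating;
- the factor is entered whatever its p-value. Three levels are needed because a high viral load means something different in a naive participant than in one failing on treatment;
- the result is a standardised risk difference with 95% CI, using small-sample robust or bootstrap standard errors. The unadjusted difference and the odds ratio that the plan already promises are reported alongside;
- the factor uses the baseline-visit sample only. That sample follows allocation, but on the same day, so allocation cannot plausibly have changed it.

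**Cost.** A short paragraph, because the arm comparison itself has to be written, and two extra parameters. Viral load, ART status and ART start date are already on the forms, so no new data, visits or participants are needed. A simple rule for missing baseline samples must be added, such as a missing category or single imputation.

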The study findings will be reported as odds ratios, confidence interval and independent variables found to have p value ≤ 0.05 at 95% confidence interval will be considered to be statistically significant in the final model.

[figure not shown]
After the final model, significant factors for ART adherence/ viral suppression will be computed.

Data Monitoring Committee:

The DMC will consist of 3 independent members with expertise in relevant clinical specialties, their responsibility is to ensure that the safety of study subjects is protected while the scientific goals of the study are being met. The previous CFL-RCT at IDI, had no major safety issues and neither were there any gender-based violence, so the DMC will suffice and will be involved in:

- Review the research protocol and plan for data safety and monitoring.

- Evaluate the progress of the trial, including periodic assessments of data quality and timeliness, participant recruitment, accrual and retention, participant risk versus benefit, performance of the trial site, and other factors that can affect study outcome.
- Make recommendations to the PI about continuation, termination, or other modifications of the trial based on the observed beneficial or adverse effects of the intervention under study.
- If appropriate, conduct interim analysis of efficacy in accordance
- Recommend solutions to address problems with study conduct, enrolment, and sample size and/or data collection.

Study visits (scheduled and unscheduled visit codes)

The total duration of the study is 18 months; follow up period is up to 12 months. The participant has a baseline visit (00.0) and is followed up at month 6 (168 days \pm 14 days) visit code 01.0, last visit is at month 12 (336 days \pm 14 days) visit code 02.0.

The participant might return at the clinic due to an illness, or repeat blood draw, this interim visit codes will be numbered sequentially from the previous scheduled visit. (00.01, 00.02 if its next to the baseline, if next to second visit, the code will be 01.01, 01.02 etc., if its next to last visit it will be coded 02.1, 02.2, etc.).

The study visit window is 2 weeks (14 days), beyond this period a visit code denoting an interim visit is given; e.g. Visit code 01.1 first contact with patient past visit 01.0 and 01.2 denotes second contact with patient past visit 01.0.

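### Seven background factors are tested at p ≤ 0.05 with no exploratory label and no fixed outcome or visit, so the factors called significant would be unreliable

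*Combined protocol and SAP*

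**What the plan says.** The rule is in section 3.4, Study Objective 2, under Bivariate Analysis and Multivariate Analysis.

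- Seven factors are listed: "independent variables (age, gender, ART duration, marital status, education status, occupation and religion").
- The chi-square screen names two outcomes: "and adherence and virological suppression will be analyzed using bivariate analysis". Entry follows from the result: "Variables found to be significant at p value of p ≤ 0.05 will be considered for the multivariable analysis".
- A second route needs no p-value: "and those considered to have a scientific explanation will be entered into the multivariable model".
- The model sentence names three outcomes and uses causal language: "Multivariable logistic regression will be used to determine the factors that influence adherence or virological suppression and retention in care".
- The model equation defines its probability as "Probability of being adherent and virally suppressed", which reads as one joint outcome.
- The final rule is that "independent variables found to have p value ≤ 0.05 at 95% confidence interval will be considered to be statistically significant in the final model". The closing sentence omits retention: "After the final model, significant factors for ART adherence/ viral suppression will be computed".

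The outcome list earlier in section 3.4 gives adherence, suppression and retention at months 6 and 12. The factor analysis does not say which visit it uses. The text gives it no exploratory label and no adjustment for the number of tests.

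**The concern.** Each null factor has roughly a 5% chance of being called significant, and the plan gives that chance to seven factors in each model, with the number of models left open. Requiring p ≤ 0.05 a second time looks like a safeguard. It is applied to the same participants, however, so a factor with a small p-value in the screen usually keeps it.

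A second problem concerns size. A factor kept because its p-value was small tends to have an estimate that is too far from 1, and its printed confidence interval takes no account of the selection.

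What is at stake is any statement about which youth fail to suppress or adhere. The plan would present such statements as significant and as influences on the outcome.

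**Working it through.** **Inputs from the plan.** Seven factors; 0.05 at both stages; two or three outcomes; months 6 and 12; 79% and 94% suppression; 93 per arm before loss to follow-up (186 evaluable); total 206.

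**The plan's own figures.** The plan gives no family-wise error rate to reproduce. Its sample size does reproduce to rounding: Kelsey 81.5 per arm (printed 81), Fleiss 81 (printed 80), with continuity correction 94 (printed 93), and 186/0.9 = 206.7 (printed 206).

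**Independent-test benchmark.** If all k tested factor effects are null, P(at least one p ≤ 0.05) = 1 − 0.95^k.

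**Simulations of the written rule, all factors null, N = 186.**

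- Simulation A: 1,500 runs per scenario, 80% success, all-binary factors or a mix of two to four levels, Wald tests with arm in the model, outcome correlation 0, 0.5 or 0.8.
- Simulation B: 1,500 runs per scenario, 86.5% success (the mean of 79% and 94%), four 2-level and three 4-level factors, likelihood-ratio tests, latent correlation 0.5.

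| Reading | k | 1 − 0.95^k | A | B |
|---|---|---|---|---|
| 1 outcome, 1 visit | 7 | 30% | 24–29% | 27% |
| 2 outcomes, 1 visit | 14 | 51% | 42–50% | 50% |
| 3 outcomes, 1 visit | 21 | 66% | 53–60% | 60% |
| 2 outcomes, 2 visits | 28 | 76% | 60–75% | not run |
| 3 outcomes, 2 visits | 42 | 88% | 74–87% | 85% |

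In the last row, A's mixed-level run finished only for uncorrelated outcomes (82%), and B gives 78–86% for correlations from 0.8 to 0.2. With 79% success, B gives 28%, 51%, 63% and 85% for 1, 2, 3 and 6 outcome-visits. The three-outcome rows screen retention like the other outcomes, which the text does not state.

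**If some factors truly matter.** With four of the seven null, two outcomes at one visit give 8 null tests: 1 − 0.95^8 = 34%. Three outcomes at two visits give 24: 1 − 0.95^24 = 71%.

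**What the second test does.** The screen alone should pass 7 × 0.05 = 0.35 null factors per model. In A, about 0.32 survive the final model with binary factors (0.32/0.35 = 92%), and 0.26 to 0.29 with mixed levels (about 74–83%). The second test removes little, but it adds no error.

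**What happens without the screen.** In B's set-up, entering all seven factors gives about 37%, against 27% with the screen. The 37% exceeds the 30% benchmark because likelihood-ratio tests run above their nominal level here. There are 186 × 0.135 = 25 expected failures for 4 × 1 + 3 × 3 = 13 factor terms, about 2 per term.

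**Inflated estimates.** Assume a balanced binary factor (93 v 93) and 13.5% overall failure.

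- True odds ratio 1.5: p ≤ 0.05 in about 15–16% of trials; median odds ratio among those about 2.8–2.9, or about 1.9 times the truth.
- True odds ratio 2.0: p ≤ 0.05 in about 35–36%; median about 3.0–3.2, or 1.5–1.6 times the truth.

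**The case against.** Five points can be made for the plan.

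1. **The number of models is not stated to be large.** The screen names two outcomes, the equation reads as one joint outcome, and no analysis sentence says factor models are fitted at both visits. This stands. A reader might infer that a false determinant is more likely than not, but the documents do not support that: it needs about three outcome-visits. The ambiguity is itself part of the defect.
2. **The global null is extreme.** Section 1.1 itself reports national suppression of 44.9% in young females and 32.5% in young males, so at least one factor may be real. This stands, and the four-of-seven calculation allows for it.
3. **Screening and re-testing do not cause the inflation.** This stands. A reader might infer that using 0.05 twice raises the error, but the number of tests does that. Deleting the screen and changing nothing else would make matters worse.
4. **Part of the remedy is already present.** The factors are named in advance, odds ratios with intervals are promised, and nothing says non-significant results will be withheld. This is true, but the final rule still sorts factors by p ≤ 0.05. Factors entered on scientific grounds are not subject to the same selection bias, so inflation should not be claimed for every estimate.
5. **Determinants are not a trial objective.** Neither the specific objectives in 1.3.2 nor the trial's research question in 2.6 asks for a quantitative determinants model, and barriers and enablers are studied qualitatively. This limits the consequence. It is also a reason to label the analysis exploratory, which the plan does not do.

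**Conclusion.** The point holds in limited form. Followed as written, the rule gives a false significant factor about 24–30% of the time for one outcome at one visit and about 42–51% for two outcomes at one visit, if all seven factors are null. Even the lowest figure is about five times 5%. The 74–88% range belongs only to three outcomes at both visits, a reading the plan leaves open but does not state. Real associations lower all these figures.

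A reader might infer that modest associations will in general be reported at nearly double their size. That is not supported. It applies only to results that reach p ≤ 0.05 when the true odds ratio is near 1.5.

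Nor does this touch the trial's type I error for CFLU against standard of care. Arm is not among the seven listed factors, and the 206 comes from a separate two-proportion calculation.

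The sizes rest on assumed factor categories and frequencies, outcome correlation, success rates of 79–86.5% and 186 evaluable participants.

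**What to change.** Amend Bivariate Analysis and Multivariate Analysis in section 3.4 as one package, because removing the screen alone raises the false-positive rate to about 37% for one outcome.

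- Replace the p ≤ 0.05 entry rule with a short factor list fixed in advance on subject-matter grounds. Keep it small: expected failures among 186 are about 25 (at 13.5%) to 39 (at 21%).
- Name the outcome and visit modelled, for example viral suppression at one named visit, and make the model equation match.
- Label the analysis exploratory.
- Report the odds ratio and 95% confidence interval for every listed factor, whatever its p-value.
- Replace the wording about influence and statistical significance with factors associated with the outcome.

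Holm adjustment is needed only if a formal significance claim is kept. With seven factors its first threshold would be 0.05/7 = 0.0071.

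The cost is a change of wording, with no new data or participants. The downside is that fewer background factors can be called significant.
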